## Analysis of Primary Outcome

The primary analysis comparing response rates will make use of the exact conditional test (ECT) version of Mantel-Haenszel methods to adjust for within-center clustering, as implemented within the Proc-StatXact software system (48). Secondary analyses of the primary endpoint will rely on logistic regression and generalized estimating equation (GEE) methods to evaluate whether observed differences, if any, are attributable to imbalances in prognostic factors such as baseline symptom severity (49). Standard regression diagnostics will be used to assess model adequacy and examine potential outlying or influential data points. In addition, time to response will be compared among groups using standard methods for failure-time data, including Kaplan-Meier curves, logrank tests, and Cox proportional hazards modeling (50).

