## 13.3 Randomization and Stratification

The nine treating Clinical Centers comprise the nine Clinical Sites. To ensure balance across treatment groups within each Clinical Site, a stratified randomization will be used. Within each of the nine strata, subjects will be randomly allocated in equal proportions to the two treatment arms using a permuted block randomization procedure with variable block sizes. In order to maintain blinding, each subject will be assigned a unique treatment identifier number. The treatment assignment code, corresponding to each treatment identifier number, will be known only to the University of Pennsylvania Medical Center Investigational Drug Service and the Data Coordinating Center Quality Assurance Director, until the completion of treatment and data collection on all

1246 participants.

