### Secondary Analyses

A number of secondary analyses will be conducted, both to evaluate the secondary symptom-related outcomes, and to supplement the primary endpoint comparison. Secondary outcomes include pain and urgency measured on the Likert scales, urinary frequency and volume measures obtained from the voiding diary, the IC Symptom and Problem Index, the University of Wisconsin Symptom Survey, the Health Status Questionnaire (MOS SF-36), and the MOS Sexual Functioning Scale. Other outcomes to

Profiles of symptom changes over time as collected from the symptom questionnaires and voiding logs will be compared among treatment groups using methods for longitudinal data analysis (51). These methods will include random effects regression models for continuous outcomes and GEE methods for categorical and ordinal outcomes (51). Both within and between-participant variability in these outcomes will be carefully assessed to provide pilot data for future clinical trials. For measures obtained only at baseline and one follow-up time point, change from baseline will be compared among groups using analysis of variance (ANOVA) and regression methods. When applicable, additional analyses of the symptom outcomes will include evaluation of time to response defined by specific changes in symptoms (e.g. 50% drop in symptom score). Associations between longitudinal changes in secondary outcomes and the overall participant assessment of improvement will be used to supplement the primary endpoint analysis and evaluate the validity of the symptom scales for assessing change.

1324 Changes in the distribution of "worst" symptoms from baseline to 34 weeks; as recorded on the symptom ranking cards, will be evaluated using a marginal homogeneity test (48).

be used in the final assessment include withdrawal rates.

Withdrawal rates will be compared among arms using standard methods for failure-time data as described above (50).

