### Biomarker Studies

 Urine specimens for biomarker studies will be collected before the first treatment, before and after the  $4^{th}$  treatment, and at the 34 week time point. Markers to be evaluated are outlined in Section 7. The primary goal of these studies is to evaluate changes in marker levels over time and evaluate the associations between these changes and both treatment and overall patient responses. Due to the large number of markers being evaluated, in order to protect against an inflation in Type I error rates due to multiple comparisons, the sample size and power calculations below utilize an overall Type I error of  $\alpha$ =0.01. It is recognized that these evaluations are primarily exploratory, and that measures that demonstrate promise as laboratory markers may require further evaluation in another clinical trial setting.

Analyses on which sample size estimates are based will consist of two primary types. The first type will involve paired comparisons of changes from baseline to 34 weeks, within subgroups defined by treatment arm and/or response to therapy (as defined by the primary endpoint). These analyses will utilize a paired t-test. The required sample sizes to detect changes of a given magnitude, in units of standard deviations of the change (s.d.), are given in the table below. The second set of analyses will compare these changes between subgroups defined by treatment arm and/or response to therapy using a two-sample t-test. The required sample sizes to detect differences in the changes, also in units of s.d., are also in the table. These calculations assume 80% power with a two-sided  $\alpha$ =0.01

, 5												
Cina of	Required Sample Sizes											
Size of	Paired t-test to	Two-Sample t-test to Compare Two Groups										
Difference	Compare Changes	1:1 Ratio	o of Group	1:2 Ratio	of Group							
(in units of s.d.)	Within a Group	S	izes	Sizes								
1.0	15	50	(25 + 25)	57	19 + 38							
0.9	18	60	(30 + 30)	69	23 + 46							
0.8	21	76	(38 + 38)	84	28 + 56							
0.7	27	98	(49 + 49)	111	37 + 74							
0.6	36	130	(65 + 65)	147	49 + 98							
0.5	50	186	(93 + 93)	210	70 + 140							
0.4	76	> 260		> 260								
0.3	130	> 260		> 260								
0.2	> 260	> 260		> 260								
0.1	> 260	> 260		> 260								

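### Randomisation is stratified by nine sites, but the t-test for marker changes and the logrank tests between arms are named without site; including it is a small, nearly free improvement

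*Protocol*

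**What the plan says.** **Allocation.** Protocol 13.3 makes Clinical Site the stratification factor: "To ensure balance across treatment groups within each Clinical Site, a stratified randomization will be used". It adds: "Within each of the nine strata, subjects will be randomly allocated in equal proportions". Permuted blocks of variable size are used.

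**Primary test.** Section 13.5 (Analysis of Primary Outcome) uses the exact conditional "version of Mantel-Haenszel methods to adjust for within-center clustering". Section 13.2 also raises the sample size by 20% for clustering within sites.

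**Other comparisons in 13.5:**
- Time to response: "standard methods for failure-time data, including Kaplan-Meier curves, logrank tests, and Cox proportional hazards modeling". No strata are named.
- Withdrawal: "Withdrawal rates will be compared among arms using standard methods for failure-time data as described above".
- Measures with one follow-up point: "change from baseline will be compared among groups using analysis of variance (ANOVA) and regression methods". Model terms are not given.
- Marker changes from baseline to 34 weeks are compared "between subgroups defined by treatment arm and/or response to therapy using a two-sample t-test". The Biomarker Studies text builds its table of required numbers and its detectable differences on this test, including an arm comparison with 65 per arm.
- Logistic regression and GEE for the primary endpoint are meant to show whether differences "are attributable to imbalances in prognostic factors such as baseline symptom severity". Site is neither listed nor excluded.

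**Standing of the list.** The opening of 13.5 describes it as an overview of methods that may be used and may be revised. Section 13.5.2 leaves details of the final analysis to a separate Data Analysis and Monitoring Plan, which is not at hand.

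**The concern.** When allocation is balanced within site, differences between sites largely cancel from the difference between arms. They do not cancel from the standard error of a test that pools all sites. Such a test reports more uncertainty than the design has: its true type I error lies below the nominal level, and it gives up a little power.

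The protocol treats site as important enough to govern the allocation, the primary test and the sample size. The two-sample t-test for markers is a fully specified method that cannot carry a site term. A logrank test can take site only as strata, and none are named. Markers are also where a site effect is plausible, because specimens are centrifuged, stabilised, divided and frozen at each study site (section 7, Appendix E). At stake is a little precision in secondary and exploratory results, and their consistency with the primary analysis.

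**Working it through.** **1. The protocol's own figures.** For 30% v 50% at two-sided 0.05 and 80% power, the continuity-corrected formula gives 103 per arm. Then 103 × 1.20 × 1.05 = 129.8, rounded up to 130 per arm and 260 in total, as stated in 13.2. The 1:1 column of the two-sample t table (two-sided 0.01, 80% power, differences of 1.0 down to 0.5 s.d.) recomputes as 24, 29, 37, 48, 65, 94 per group, against the stated 25, 30, 38, 49, 65, 93. Both reproduce.

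**2. Intraclass correlation (ICC).** None is given. If the 20% allowance is read as a design effect over nine equal sites, ICC = 0.20 / (260/9 − 1) = 0.20 / 27.9 = 0.0072. With the unadjusted 206 patients it is 0.20 / (206/9 − 1) = 0.0091. This value concerns the binary primary endpoint. For markers and times to event the documents give nothing, so 0.05 and 0.10 are assumptions that show the range.

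**3. Two-sample t-test, formula.** With arms balanced within site:
- ratio of unadjusted to site-adjusted standard error: k = 1/√(1 − ICC)
- true type I error at nominal α: 2 × [1 − Φ(z × k)], with z = 1.960 for 0.05 and 2.576 for 0.01, the level used for markers

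| ICC | k | Excess SE | Type I at 0.05 | Type I at 0.01 |
|---|---|---|---|---|
| 0.0072 | 1.0036 | 0.4% | 0.049 | 0.0097 |
| 0.05 | 1.0260 | 2.6% | 0.044 | 0.0082 |
| 0.10 | 1.0541 | 5.4% | 0.039 | 0.0066 |

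**4. Check by simulation** (260 patients, nine sites, permuted blocks, 4000 runs per ICC, Monte Carlo error about 0.003 on the error rates):

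| ICC | SE ratio | t-test type I | Site-adjusted model | Logrank, unstratified | Logrank, stratified |
|---|---|---|---|---|---|
| 0.0072 | 1.003 | 0.049 | 0.049 | 0.054 | 0.056 |
| 0.05 | 1.022 | 0.046 | 0.050 | 0.045 | 0.049 |
| 0.10 | 1.048 | 0.040 | 0.049 | 0.040 | 0.049 |

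The direction agrees. The simulated ratios lie a little below the formula because only nine sites contribute: replacing the site share by 8/9 of itself at ICC 0.10 gives √[(0.90 + 0.10 × 8/9)/0.90] = 1.048. At 0.0072 nothing can be told from noise.

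**5. Cox model** (true log hazard ratio 0.588, 400 runs per ICC). At ICC 0.10 the unstratified estimate averages 0.573 and the stratified one 0.593; the model standard errors are 0.2045 and 0.2058. At ICC 0.0072 the estimates are 0.583 and 0.584, and the standard errors 0.2054 and 0.2063. Leaving out site pulls the estimate slightly toward no effect. Stratifying does not narrow the interval.

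**6. Gain for markers.** With 65 per arm, a difference of 0.6 s.d. and α = 0.01, and taking the tabulated s.d. as the total s.d., power is 80.1% without site. With site in the model it would be 80.4%, 82.5% or 84.8% at the three ICCs.

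**The case against.** The strongest objection is that silence is being read as a decision. Section 13.5 is an expressly revisable overview, details go to a document not shown, and the terms of secondary models are normally settled there. For ANOVA, regression, GEE, logistic and random-effects models this stands in full: a reader might infer that they ignore site, but nothing says so, and site would fit in each. It stands only in part for the two-sample t-test, which the protocol names and uses for sample sizes and which cannot carry site, and for the logrank test, which is named without strata.

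Further limits also stand:
- A reader might infer that every interval is too wide. For Cox that is wrong (step 5).
- A reader might infer a loss from the planned 80% power. That would require the s.d. in the marker table to be a within-site s.d., which the protocol does not say. Read as a total s.d., the unadjusted test keeps its planned power, and what is missed is a gain.
- The same marker t-test also compares responders with non-responders. These are not randomised groups, so the argument does not reach them.
- Many outcomes are changes from baseline, in which stable site differences subtract out, so the relevant ICC may be small.
- Any error is conservative, and the analyses are secondary or, for markers, described as primarily exploratory.

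**Conclusion.** The point holds as a minor improvement. Site governs the allocation and the primary test, but the marker t-test and the logrank tests between arms are named without it. If site is prognostic, those tests are slightly conservative. At the ICC implied by the protocol's own allowance the excess in the t-test standard error is about 0.4%, which is immaterial. It reaches 2.6% to 5.4% only under assumed ICCs of 0.05 to 0.10, for which the documents offer no source. For Cox the consequence is slight attenuation. The primary test, the total of 260, and every stated sample size and power figure are unaffected, and no conclusion of the trial is put at risk.

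**What to change.** Add one sentence to Protocol 13.5: secondary and marker comparisons between the randomised arms will be stratified by Clinical Site (logrank, Cox) or include site as a fixed effect (ANOVA, regression, and a linear model in place of the two-sample t-test for marker changes). Limit it to comparisons of randomised arms, so that responder v non-responder comparisons are not covered. The marker table can stay as it is.

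The cost is wording plus eight degrees of freedom for nine sites: out of 260 − 2 = 258 for full-sample outcomes, or 130 − 2 = 128 for markers at 65 per arm. It also settles in advance a choice that would otherwise stay open.

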### Secondary Analyses

A number of secondary analyses will be conducted, both to evaluate the secondary symptom-related outcomes, and to supplement the primary endpoint comparison. Secondary outcomes include pain and urgency measured on the Likert scales, urinary frequency and volume measures obtained from the voiding diary, the IC Symptom and Problem Index, the University of Wisconsin Symptom Survey, the Health Status Questionnaire (MOS SF-36), and the MOS Sexual Functioning Scale. Other outcomes to

Profiles of symptom changes over time as collected from the symptom questionnaires and voiding logs will be compared among treatment groups using methods for longitudinal data analysis (51). These methods will include random effects regression models for continuous outcomes and GEE methods for categorical and ordinal outcomes (51). Both within and between-participant variability in these outcomes will be carefully assessed to provide pilot data for future clinical trials. For measures obtained only at baseline and one follow-up time point, change from baseline will be compared among groups using analysis of variance (ANOVA) and regression methods. When applicable, additional analyses of the symptom outcomes will include evaluation of time to response defined by specific changes in symptoms (e.g. 50% drop in symptom score). Associations between longitudinal changes in secondary outcomes and the overall participant assessment of improvement will be used to supplement the primary endpoint analysis and evaluate the validity of the symptom scales for assessing change.

1324 Changes in the distribution of "worst" symptoms from baseline to 34 weeks; as recorded on the symptom ranking cards, will be evaluated using a marginal homogeneity test (48).

be used in the final assessment include withdrawal rates.

Withdrawal rates will be compared among arms using standard methods for failure-time data as described above (50).

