### 6.2.1 Inclusion Criteria

- 1. At least 18 years of age.
- 2. Participant must sign and date the informed consent.
- 3. Participant must have received a minimum of 12 weeks of treatment with some standard form of therapy or combination of therapies for IC. The treatment must have occurred after diagnosis of IC and administered in response to the patient's IC symptoms. Potential previous therapies include: tricyclic antidepressants, hydroxyzine, other antihistamines, DMSO, pentosanpolysulfate, heparin, NSAIDS, and anticholinergies.
- 4. Participant (male or female) must agree to use a medically approved method of birth control.
- 5. Participant must report a urinary frequency of at least 11 times per 24-hour day, on average over the previous four weeks. This frequency criterion must be met at each of the two baseline-screening visits as reported by the participant.
- 6. Participant must report a pain/discomfort score of 4 or greater on a 0 9 Likert scale. This pain/discomfort criterion must be met at each of the two baseline-screening visits.
- 7. These reported urinary symptoms of frequency and pain/discomfort must have been present for at least the previous 24 weeks prior to the first baseline screening visit.
- 8. Participants must report in the baseline voiding diary at least one voided volume greater than or equal to 75cc in a 24 hour period.

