### 13.2 Sample Size Calculations

1221 1222

1223

1224

1225

1226

1227 1228 The baseline response rate for the intravesical saline placebo of 30% is based on previous IC studies, and other studies suggesting that this is a typical placebo rate for symptom-related outcomes. Assuming 80% power to detect the specified difference between groups at a two-sided  $\alpha = 0.05$  level of significance using the Fisher's exact test, a total of 260 participants (130 per arm) are required. This proposed sample size includes adjustments for clustering within clinical sites (20% increase), and interim monitoring (5% increase). Total required sample sizes for alternative response rate differences are shown in the table below.

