## ICCTG Protocol #2 – Visit Schedule (Weeks) Phase I – Randomized, Double-Blind Study

## **APPENDIX B**

		ening sits	Treatment Phase 6 Treatments in 10 Weeks				Post-Treatment Follow-up Phase 24 Weeks (6 Months)								
			RX	RX	RX	RX	RX	RX	Phone Visit	Phone	Clinic	Phone	Clinic	Phone	Clinic
Event	B1 -4	B2 -1	1	2	3	4	5 *	6 *	(optional)	Visit	Visit 18	Visit 22	Visit 26	Visit 30	Visit 34
Week	-4	-1	1*	*	*	*	*	*	10, 11, or 12	14					
Visit Number	1	2	3	4	5	6	7	8	9	10	11	12	13	14	15
Consent Form	Χ														
Clinic Visit	Χ	Χ	Χ	Χ	Χ	Χ	Χ	Χ			Χ		X		Χ
Treatment Follow-Up Phone Call									~	~		~		*	
Day 1 Follow-up (PHNTP)			2	A		A									
Day 2 Follow-up (PHNTP)			*	A		A									
Patient Contact Information (PTCONT)	Χ														
Medical History (MED)	Χ														
Voiding Diary (VOID)		$X^3$									$X^3$		$X_3$		$X^3$
Demographics (DEMO)	Χ														
Eligibility Confirmation (ELIG)	Χ	Χ													
Randomization (RAND)		Х													
Patient's Daily Medication Diary (PTDIARY)	X 3	X 	X 	X 	$X_3$	X 	$X_3$	X 			X³				X 3
Medication Diary Record (CMED)		Х	Х	Х	Х	Х	Х	Х			Х				Х
Instillation/Dosing Information (DOSE)			Х	Х	Х	Х	Х	Х							
Adverse Event/Serious Adverse Event (AE)			Х	Х	Х	Х	Х	Х	Х	Х	Х	Х	Х	Х	Х
Contraceptive Use (DOSE and STVISIT)			Х	Х	Х	Х	Х	Х	Х	Х	Х	Х	Х	Х	Х
Unmasking Record (UNMASK) 															-
Treatment Stop Point I (TSTOPI) 								Χ							·
Study Stop Point I (SSTOPI) 															X
Patient Transfer (TRANS) 															
Study Close-out (STCL) 															X
Patient Close-out (PTCL) 															Х
SYMPTOM QUESTIONNAIRES:															
Baseline Symptoms (BSYM1&2)	Х	Х													
Follow-up Symptoms (FUSYM)								Χ			Х		Χ		Х
IC Symptom & Problem Index (SYMPROB)		Х						Х			Х		Х		Х
Health Status Questionnaire (SF36)		Х		1				Χ			Х		Χ		Х
MOS Sexual Functioning Scale (MOS)		Χ						Χ			Х		Х		X

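### The only analysis named for the 'worst' symptom outcome is a before-after test that does not use treatment arm, so it cannot support or rule out a BCG-versus-saline difference

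*Protocol*

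**What the plan says.** Section 13.5, Secondary Analyses, gives these analyses two purposes: "both to evaluate the secondary symptom-related outcomes, and to supplement the primary endpoint comparison". It then assigns methods by type of outcome:

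- Repeated symptom measures: "Profiles of symptom changes over time as collected from the symptom questionnaires and voiding logs will be compared among treatment groups".
- Measures with baseline and one follow-up: "change from baseline will be compared among groups using analysis of variance (ANOVA) and regression methods".
- Withdrawal: "Withdrawal rates will be compared among arms using standard methods for failure-time data".
- The 'worst' symptom: changes in its distribution, i.e. "symptoms from baseline to 34 weeks; as recorded on the symptom ranking cards, will be evaluated using a marginal homogeneity test".

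The first three name a contrast between groups or arms. The fourth names none. The worst symptom is not in the list of secondary outcomes in 13.5, nor is it named in 4.4.2.

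**The concern.** A marginal homogeneity test takes each patient's baseline and week-34 category and asks whether the two marginal distributions are equal. Arm is not an input. Objective 1 in section 2 is BCG against sham on symptoms, and one stated purpose of the secondary analyses is to supplement that comparison. For this outcome the named method answers a different question: whether the distribution moved over time.

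Two misreadings follow. A pooled significant result could be taken as support for BCG when both arms moved alike. A pooled null could be taken as no treatment effect when the arms moved in opposite directions. Running the test in each arm does not cure this, because setting two before-after p-values side by side is not a test of the difference between arms.

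**Working it through.** **No figure to reproduce.** The protocol gives no number for this analysis. The main conclusion follows from the form of the test; the simulation only illustrates it.

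**Form of the test.** For K categories, let d be the first K−1 differences between baseline and week-34 totals. Let V have diagonal entries n(i.) + n(.i) − 2n(ii) and off-diagonal entries −(n(ij) + n(ji)). The Stuart-Maxwell statistic is d′V⁻¹d, referred to chi-square with K−1 degrees of freedom. Only the baseline-by-week-34 table enters.

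**Inputs.** From the protocol: 130 per arm (13.2), and up to 15% withdrawal (13.4), so 130 × 0.85 = 110.5, taken as 110. Assumed: three categories; baseline shares 50/30/20%; 40% of patients keep their category and 60% are redrawn; two-sided 5%; 5,000 replicates. The between-arm comparator is a Wald test of the arm difference in change of category shares. It stands in for the stratified test proposed below, whose power may differ.

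**Implied week-34 shares** (0.4 × baseline + 0.6 × redraw):

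- Common shift, redraw 30/30/40: 0.20 + 0.18 = 38%; 0.12 + 0.18 = 30%; 0.08 + 0.24 = 32%. The first category falls 12 points in both arms.
- Opposite shifts: BCG, redraw 70/25/5, gives 62/27/11%. Saline, redraw 30/35/35, gives 38/33/29%. The pooled average is (62+38)/2 = 50, (27+33)/2 = 30, (11+29)/2 = 20, exactly the baseline, although the arms differ by 24 points in the first category.

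**Share of simulated trials with p < 0.05**

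| Setting | n per arm | Pooled | BCG only | Saline only | Between arms |
|---|---|---|---|---|---|
| No shift | 130 | 5.4% | 4.9% | 4.4% | 4.8% |
| Same shift in both arms | 130 | 97.8% | 77.5% | 77.0% | 5.4% |
| Shift in BCG arm only | 130 | 49.1% | 78.3% | 4.6% | 50.6% |
| Opposite shifts | 130 | 3.9% | 82.8% | 68.0% | 97.4% |
| Same shift in both arms | 110 | 94.6% | 67.2% | 68.9% | 5.2% |
| Opposite shifts | 110 | 5.7% | 75.7% | 58.3% | 93.5% |

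With no shift the test holds its level, so it is sound for its own null. In the common-shift rows that null is false, so the high figures are power to detect change over time.

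**Range for the common shift.** A second set of assumptions (baseline 40/30/30%, 60% keep their category) gives pooled rejection at n = 260 of 31.6%, 85.8% and 99.5% for common falls of 5, 10 and 15 points. At n = 130 in one arm it gives 16.5%, 55.7% and 86.9%. A between-arm chi-square test stays at 4.4–6.1%.

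**Why within-arm results do not substitute.** Take the common-shift row at 130 per arm, with independent arms and no arm difference. The chance that BCG is significant and saline is not is 0.775 × (1 − 0.770) = 0.178. The reverse is (1 − 0.775) × 0.770 = 0.173. The arms disagree in about 35% of such trials although they are identical.

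**Is an arm contrast supplied elsewhere?** The longitudinal and GEE methods are tied to questionnaires and voiding logs. ANOVA on change needs a numeric change, which an unordered category lacks. Section 13.6 names software for exact tests between groups but assigns none to this outcome. By contrast, 13.5 Biomarker Studies plans paired within-group tests and then a between-group comparison. The worst-symptom outcome gets only the first of those two steps.

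**The case against.** The sentence asks about change from baseline to week 34, and the test fits that question. Objective 3 and section 4.4.2 make the study of symptom measures over time an aim in itself. The outcome is not a listed secondary endpoint. Section 13.5 presents its methods as an overview that may be revised, and 13.5.2 defers detail to the Data Analysis and Monitoring Plan. If the ranking item sits inside a symptom questionnaire, the between-group GEE analysis could cover it.

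Much of this stands: the test is valid as description, and the consequence is small. What remains is that the protocol names one method for this outcome and that method has no arm contrast. A general permission to revise does not add one, and the text ties the outcome to ranking cards without linking them to a questionnaire.

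Three stronger readings are tempting and are not supported:

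- A reader might infer that a significant result is to be expected even if BCG does nothing. Section 13.2 takes 30% saline response from previous IC studies and "other studies suggesting that this is a typical placebo rate for symptom-related outcomes". That is a rate of response, not of change in which symptom ranks worst, and a patient can improve without any change in ranking. Eligibility thresholds on pain and frequency at both baseline visits make some common shift possible, but no document figure fixes its size.
- A reader might take the simulated percentages as false-positive rates. Under a common shift the test correctly rejects a null of no change.
- A reader might infer that the ranking cards have no data source because Appendix B has no row for them. Appendix B lists forms, not items, and the global assessment question behind the primary endpoint has no row either.

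**Conclusion.** The point holds in a limited form. As the only method named for the worst-symptom outcome, the marginal homogeneity test describes change over time and cannot support or rule out a treatment difference, whether pooled or run by arm. This follows from the form of the test and needs no assumption about shifts. The illustrated extremes at 130 per arm (97.8% pooled rejection with identical arms; 3.9% with opposite shifts that a between-arm test detects in 97.4%) rest entirely on assumed shares and shifts. The primary endpoint, sample size, interim boundary and listed secondary outcomes are unaffected. It is a small correction that is worth making because it prevents a before-after p-value from being read as evidence about BCG.

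**What to change.** In 13.5, Secondary Analyses, add one sentence: the week-34 'worst' symptom category will be compared between arms, stratified by baseline category, with a generalized Mantel-Haenszel test (exact or Monte Carlo if cells are sparse). A multinomial regression on arm and baseline category is an alternative. State that the marginal homogeneity test is kept as a within-arm description only and that no treatment claim will be drawn from it.

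The Mantel-Haenszel approach is close to the method already planned for the primary outcome. The cost is one additional exploratory analysis, to be labelled as such, with no extra patients, visits or sample-size change.
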